9.4 Pharmacodynamic Assessments and Biomarker Analysis

Whole blood samples will be drawn and biopsy material will be collected for assessment of PD and biomarker analysis at the time points indicated in the Blood Sampling Schedule ([Table 7-3](#) and [Table 7-4](#)). Blood samples will be processed to collect serum.

Assessment of immunophenotyping, soluble PD-L1, soluble 4-1BB, cytokine efficacy panel, receptor occupancy (RO), PD-L1 immunohistochemistry (IHC), tumor mutational burden (TMB), TCR clonality sequencing, microsatellite instability (MSI) and mRNA/IF may be adjusted for Part B, following availability of Part A data. Conduct of RO assay (for Part A and B) will be dependent on availability of a suitable assay.

Characterization of exposure-dependent PD markers of target and pathway engagement assessed in Part A and the optional Part A-2 (if applicable) will be core elements of selecting up to 4 dose levels of NM21-1480 that are at or below the MTD for determination of the RP2D in Part B. In mCRC patients enrolled to Cohort B8, additional biomarker/PD marker, including, e.g., assessment of ctDNA levels, determination of MHC-I expression on tumor cells; or specific mutational analysis including e.g., BRAF, KRAS, NRAS, POLE, PIK3CA, PTEN, APC, p53 may be conducted.

10 STATISTICAL METHOD AND SAMPLE SIZE CALCULATION

10.1 General Considerations

A detailed statistical analysis plan (SAP) will be prepared by the Sponsor or designee. This plan may modify the statistical methods outlined in the protocol; however, any major modifications of the primary endpoint definition or analysis will also be described in a protocol amendment.

10.2 Sample Size Estimate Calculation

No formal group size calculation has been applied as the sample size during dose-escalation cannot be precisely determined but depends on the observed toxicity.

For Part A, dose-escalation cohorts, a BOPIN design with a pre-specified maximal patient number of 25 will be applied.

The optional Part A-2 may only be initiated after Part A is complete (i.e., the MTD for Part A has been determined). Up to 40 patients across dose levels may be enrolled to further study the exposure-dependent PD response relationship for NM21-1480 to further explore different dose levels and/or dosing intervals in parallel to Part B to complement the PK, immunogenicity and PD data to be provided by Part B.

For Part B, Cohorts B1 through B4 and B6 through B8 a BOP2 design will be applied (see [Section 10.3.2](#)) and a maximum of 40 patients will be enrolled to each cohort to assess clinical response. For Part B, Cohorts B1 through B4 and B6 through B8, an interim analysis for futility

is planned, depending on recruitment and availability of data. The interim analysis is planned after enrollment and treatment of 25 patients in a given cohort according to the BOP2 design. This futility analysis will be conducted based on availability of response data following completion of the first 2 RECIST 1.1 (and iRECIST) assessments (i.e., after 12 weeks) for the 25 patients. The 800mg flat dose of NM21-1480 will be further studied as sole dose level in Part B based on results of Part A and as per recommendation by the SMC. The Sponsor in consultation with the SMC will determine at this point of futility analysis whether the cohort shall be stopped or continued. If (a) cohort will not be stopped due to futility after the interim analysis, the study will continue with an estimated total of 40 patients to be enrolled by cohort; a final futility/clinical activity analysis based on pre-specified criteria will be conducted at this point and the Sponsor will consider continued development of NM21-1480 in a given indication. For Cohort B8, the Sponsor will hold enrollment to the cohort after 25 patients have received at least one dose of NM21-1480 treatment until all relevant safety, efficacy, PK, immunogenicity and most prominently all relevant PD data that has accrued until then has been reviewed by the Sponsor and the SMC. After this interim review, the Sponsor may decide to stop the cohort, to continue with full enrollment of the cohort or revise eligibility criteria before the remaining 15 patients in that cohort are enrolled.

For Cohort B5, a total of approximately 200 patients with head and neck squamous cell cancer may ultimately be randomized 2:1 to either NM21-1480 plus a PD-1 standard-of-care first-line checkpoint inhibitor or to the standard-of-care PD1 checkpoint inhibitor monotherapy. Based on 10,000 trial simulations performed in R, a sample size of 180 patients in a 2:1 randomization provides approximately 90% power to detect a difference of 15% between the treatment groups with an estimated two-sided Type 1 error rate <0.05 of 0.0391 ([Table 10-1](#)). Based on 10,000 simulations, the margin of error is approximately $\pm 0.4\%$ for the Type 1 error calculations. Allowing for 10% losses to follow-up, at least 200 subjects will be randomized in Cohort B5.

Table 10-1 Sample size, power and Type 1 error

Sample Size	Power	Type 1 error
60	72.16%	5.3%
72	77.96%	5.42%
84	82.01%	5.14%
96	84.33%	4.84%
108	86.27%	4.78%
120	87.57%	4.68%
132	88.06%	4.38%
144	88.58%	4.2%
156	89.46%	4.38%
168	89.72%	4.07%
180	90.07%	3.91%
192	90.36%	3.62%
204	90.43%	3.69%

An interim analysis will be performed after a minimum of 60 patients (40 patients in the NM21-1480 arm) have been enrolled. At this point recruitment will be paused, the accumulated data analysed and regulatory authorities consulted. Cohort B5 will be regarded as futile (non-binding) if the probability of observing a difference in estimated effects between control and treatment of at least 15% is less than 0.1. However, as with the other cohorts, decisions at the interim point will be taken based on clinical and regulatory input and not formal statistical testing.

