10.6.2.1 Primary Efficacy Analysis, Cohort B5

For Cohort B5, the primary efficacy endpoint will be central RECIST 1.1 read of ORR. The primary analysis will be performed in the Efficacy Analysis Set using a Bayesian logistic regression model with treatment and (CPS ≥ 1 ; CPS ≥ 20) as a covariates:

$$\text{Logit} (p_i) = \beta_0 + \beta_1 \times \text{treatment} + \beta_2 \times \text{CPS20}$$

The following prior distributions have been assumed:

$\beta_0 \sim N(-1.45, 0.16^2)$, equivalent to a control response rate of 20 ($\pm 4\%$) observed in the KEYNOTE-048 study with pembrolizumab;

$\beta_1 \sim N(0,1)$, vague prior on treatment equivalent to expected treatment difference of 0% (95% confidence interval: -16% to +43%, which corresponds to a $N(0,1)$ prior on logistic scale)

$\beta_2 \sim N(0, 0.1^2)$, vague prior on CPS effect, based on KEYNOTE-048 study with pembrolizumab, where a 0%-3% difference in response was observed across CPS levels.

The Bernoulli likelihood is not conjugate to the normal priors on the regression coefficients and so the posterior distribution of regression coefficients is not known. Let $\beta = (\beta_0, \beta_1, \beta_2)$.

$$\pi(\beta|data) \propto \pi(data|\beta)\pi(\beta)$$

In order to avoid the use of Monte Carlo methods for inference on parameters (and the requirement of large simulations to estimate posteriors with sufficient precision) we fit Laplace approximations to posterior distributions. We approximate $\pi(\beta|data) \approx N(\beta', Var(\beta'))$ where β' is the mode of the posterior distribution of $\pi(\beta|data)$ with $Var(\beta')$ the posterior covariance matrix estimated at this mode.

At the interim analysis, Cohort B5 will be regarded as futile (non-binding) if the probability of observing a difference in estimated effects between control and treatment of at least 15% is less

than 0.1. However, as with the other cohorts, decisions at the interim point will be taken based on clinical and regulatory input and not formal statistical testing. Statistical superiority of the treatment in the final analysis will be concluded if $Pr(\beta_1 > 0 | data)$ is > 0.95 .

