6 CHANGES FROM PROTOCOL-SPECIFIED STATISTICAL ANALYSIS

Only limited patients were enrolled onto the study under Cohort B1 (5 patients), Cohort B7 (5 patients) and Cohort B8 (10 patients) in Part B. Cohort A-2 only enrolled 5 patients. There are no patients enrolled under Cohort B2, Cohort B3, Cohort B4, Cohort B5 and Cohort B6 in Part B. Therefore, due to the limited data, only related TFLs will be generated and no interim analyses were performed.

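### Cohort B5's two-sided Type 1 error of 0.0391 is a one-sided figure at an unstated control rate, and it fits the 90% power only if the non-binding futility stop is obeyed

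*Protocol*

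**What the plan says.** Protocol section 10.2 states that "a sample size of 180 patients in a 2:1 randomization provides approximately 90% power". The effect to be detected is 15 percentage points in response rate, and the accompanying false-positive rate is given as "an estimated two-sided Type 1 error rate <0.05 of 0.0391". The synopsis carries the same error figure. Table 10-1 lists 13 sample sizes from 60 (power 72.16%, error 5.3%) to 204 (90.43%, 3.69%); N=180 shows 90.07% and 3.91%. The results come from 10,000 simulated trials, with a margin of about ±0.4 points on the error. Neither place gives the simulated control response rate, the CPS mix or the handling of the interim.

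Section 10.6.2.1 sets the model and the decision rule. The intercept prior is N(-1.45, 0.16²), described as "equivalent to a control response rate of 20" (±4%). The treatment prior is N(0, 1) and the CPS prior is N(0, 0.1²). "Statistical superiority of the treatment in the final analysis will be concluded if" the posterior probability of a positive treatment coefficient is above 0.95.

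After Table 10-1, section 10.2 places an interim at 60 patients (40 on NM21-1480): "Cohort B5 will be regarded as futile (non-binding) if the probability of observing a difference in estimated effects" of at least 15% is below 0.1. It adds that interim decisions will not rest on formal testing.

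SAP section 6 records: "There are no patients enrolled under Cohort B2, Cohort B3, Cohort B4, Cohort B5 and Cohort B6 in Part B".

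**The concern.** There are three separate difficulties.

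- **Sidedness.** The success rule looks at one tail only, with a nominal 5%, and there is no rule in the other direction. A reader who sees a two-sided rate below 0.05 expects roughly 2.5% in favour of NM21-1480; the figure given is 3.91% in that direction.
- **Control rate.** The intercept prior is tight. If the true control rate lies above the prior centre, the model pulls the control estimate down and credits the excess to treatment. The error therefore has no single value, yet the text gives one bound without naming the control rate behind it.
- **Futility.** Obeying a futility stop lowers both power and false positives. A Type 1 error that takes credit for a stop the sponsor may override is not controlled at that level.

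This text is the quantitative justification for randomising about 200 patients in the trial's only randomised cohort.

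**Working it through.** **Inputs.** Priors, Laplace approximation and success rule from section 10.6.2.1; N=180 split 60 control and 120 treated, a 15-point difference, and an interim at 20 and 40 from section 10.2. Two readings are needed. The futility probability is taken as a posterior probability, and the true control rate is varied because it is not stated. The main calculation enumerates all outcomes exactly with the CPS term dropped.

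**Weight of the prior.** The centre is 1/(1+e^1.45) = 19.0%. Effective sample size = (1/0.16²)/(p(1−p)) = 39.06/0.1539 = 254 at 19%, or 39.06/0.16 = 244 at 20%, against 60 controls. One prior SD up is logit −1.29, or 21.6%.

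**Reproducing Table 10-1.** A control rate of 20.85% was chosen to match the N=180 error (power / error, %):

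| N | Table 10-1 | Stop obeyed | Stop ignored |
|---|---|---|---|
| 60 | 72.16 / 5.3 | 71.3 / 5.5 | 71.3 / 5.5 |
| 120 | 87.57 / 4.68 | 86.1 / 4.6 | 91.9 / 6.0 |
| 180 | 90.07 / 3.91 | 89.1 / 3.91 | 97.7 / 6.2 |
| 204 | 90.43 / 3.69 | 89.4 / 3.5 | 98.4 / 5.9 |

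Over all 13 rows with the stop obeyed, power is within 1.6 points and error within 0.41 points of the table. The shape matches too: power flattens near 90% and error falls as N grows. With the stop ignored, power keeps climbing and error stays near 6%.

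**Could the pair arise with the stop ignored?** At N=180, error near 3.9% needs a control rate just under 20% (3.87% at 19.8%), where power is 96.6%. Power of 90% needs a control rate of 16–17% (89.9% at 16.5%), where error is 0.6%. No fixed control rate gives both. A wider search by simulation with the CPS term, over control rates of 15–26% and one- and two-tailed thresholds of 0.95 and 0.975, missed the table by at least 7 power points in some row whenever the stop was ignored.

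**One-sided error and power for +15 points at N=180** (stop ignored / obeyed, %):

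| True control rate | Error | Power |
|---|---|---|
| 16% | 0.4 / 0.2 | 88.3 / 70.8 |
| 18% | 1.5 / 0.9 | 93.7 / 79.8 |
| 20% | 4.2 / 2.6 | 96.9 / 86.8 |
| 21.6% | 8.4 / 5.4 | 98.3 / 90.9 |
| 22% | 9.8 / 6.4 | 98.6 / 91.7 |
| 24% | 18.8 / 13.1 | 99.4 / 95.1 |

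Error crosses 5% at 20.35% (ignored) and 21.4% (obeyed).

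**Check with the CPS term.** Assuming 30–60% of patients have CPS ≥20, simulation gives 4.1–4.2% at 20% control (ignored), and at 24% control 17.3–18.4% (ignored) and 12.4–12.8% (obeyed).

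**Both tails.** At 20.85% control with the stop ignored, the lower tail adds 1.0 point: 6.2 + 1.0 = 7.2%. With the stop obeyed, the lower tail is about 0.001%.

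**The case against.** - **The handling of futility in Table 10-1 is inferred.** This stands. The protocol does not say how the interim was simulated, and 20.85% is a fitted value. The fit is also not within simulation error: at that rate all 13 powers fall below the table, by up to about 1.5 points, against a margin of about ±0.6 points for 10,000 runs. Dropping the CPS term, or reading the futility probability as predictive, could account for some of this. The sponsor's exact code has not been recovered. The misfit is still small beside the gap of more than 7 power points with the stop ignored.
- **At 20% control the bound holds.** True: 4.2% ignored and 2.6% obeyed. Averaged over the protocol's own intercept prior, error is 4.6% ignored and 3.0% obeyed. Under that prior, the control rate exceeds 20.35% with probability about 30%, 21.4% about 18%, and 24% about 3%, so the 24% figures are a tail case. Dependence on the control rate is expected with a declared informative prior. The fault is stating a bound without its conditions, not using the prior.
- **The label does not alter the number if the stop is obeyed.** Correct, because the lower tail is then negligible. It still contradicts the success rule, and with the stop ignored the two-sided rate is about 7%.
- **Nothing depends on it now.** B5 enrolled nobody, and the SAP plans no hypothesis tests or interim analysis. That limits the consequence, but the design statement remains wrong as written.

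**Conclusion.** The concern holds. The 0.0391 is a one-sided rate and is about right as such for a control rate near 20–21%. It goes with 90% power only when the futility stop is treated as binding, which the protocol says it is not. Ignoring the stop at the matching control rate raises the one-sided error from 3.91% to 6.2%. The bound of 0.05 fails above about 20.4% control (ignored) or 21.4% (obeyed), both inside the range the protocol gives for its control rate. The stated power is conditional too: with the stop obeyed it is 70.8% at 16% control and 86.8% at 20%.

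The conclusion rests on the stated priors and success rule, a posterior reading of the futility rule, a fixed true control rate and an assumed CPS mix. That no other handling produces the table is shown for the variants tried; it is not proved in general. The point corrects a design figure and changes no analysis performed.

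**What to change.** 1. In section 10.2 and the synopsis, change two-sided to one-sided.
2. Beside Table 10-1, state the control response rate, the CPS mix and the futility handling that were simulated.
3. Replace the unconditional bound with a short table of Type 1 error and power for control rates of 16–24%, with the non-binding stop ignored and obeyed.

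A higher posterior threshold or a down-weighted intercept prior is an optional design choice. If either is adopted, power should be restated under the same futility handling.

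The cost is a re-run of the existing simulation over a few control rates and wording in two places. The reported figures will look less favourable. There is no operational cost, because the cohort enrolled no patients.

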10.6.2.3 Objective Response Rate

Objective response rate (ORR) is defined as the number of patients achieving an overall best response of CR or PR divided by the total number of patients. Two sets of ORR will be summarized, 1 for confirmed and 1 for confirmed + unconfirmed responses. A 2-sided exact 95% confidence interval based on the Clopper-Pearson method will be provided for ORR ([Clopper and Pearson, 1934](#)).

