3 STATISTICAL METHODOLOGY

3.1 General Considerations

3.1.1 *Analysis Groupings*

Unless specified otherwise, analyses for Part A will be presented by dose level and in total, analysis for Part A-2 will be presented in total, and analysis for Part B will be presented by cohort and in total. Additionally, for the analysis of demographic, safety, PK, and immunogenicity data, a total for all patients across Part A and Part A-2 will be presented, as will a total for all Part B patients who received NM21-1480, and a total for all patients in any part who received NM21-1480 at the 800 mg dose level.

3.1.2 *Analysis Day*

Analysis day will be calculated from the date of first dose of study treatment. The day of the first dose of study drug will be Day 1, and the day immediately before Day 1 will be Day -1. There will be no Day 0.

3.1.3 *Definition of Baseline*

Baseline is defined as the last measurement prior to the start of study treatment.

3.1.4 *Summary Statistics*

Categorical data will generally be summarized with counts and percentages of subjects. The denominator used for the percentage calculation will be clearly defined. Continuous data will generally be summarized with descriptive statistics including n (number of non-missing values), mean, median, standard deviation, minimum, and maximum.

3.1.5 *Hypothesis Testing*

No hypothesis testing will be provided.

3.1.6 *Evaluation of Site Effect*

Site effect will not be analyzed.

3.1.7 *Handling of Missing Data*

Unrecorded data values will be recorded as missing. Only recorded (i.e. complete) data values will be used for statistical analyses. In general, invalid or missing values will not be imputed unless stated otherwise.

- For BOR and ORR, patients in the Efficacy Analysis Set who do not have sufficient on-study tumor assessments to characterize response will be included in the denominator when calculating BOR percent and ORR, and will thus be treated as non-responders. Further details are found in section [3.4.1.1](#).
- In cases of missing or incomplete dates (e.g. AEs and concomitant medications or procedures), the missing component(s) will be assumed as the most conservative value possible. For the detailed missing/partial data handling conventions for treatment-emergent adverse events see Table 2 in Appendix A. The actual data values as they appear in the original case report forms (CRFs) will be presented in the data listings.

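### Cohort B5 goes from 180 to 200 as if lost patients leave the analysis, but dosed patients lost before a documented response stay in it as non-responders, so the power at 200 needs restating

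*Protocol*

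**What the plan says.** Protocol section 10.2 says that "a sample size of 180 patients in a 2:1 randomization provides approximately 90% power to detect a difference of 15% between the treatment groups". It puts the type 1 error at 0.0391 and calls it two-sided. Table 10-1 prints 90.07% power and 3.91% type 1 error at 180. The section then adds the loss allowance: "Allowing for 10% losses to follow-up, at least 200 subjects will be randomized in Cohort B5". The synopsis repeats this.

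Four passages decide what happens to a lost patient:

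- Protocol 10.6.2.1: "The primary analysis will be performed in the Efficacy Analysis Set". Section 10.4.4 defines that set as dosed patients with measurable baseline disease. Its only Part B exclusion is for patients still on treatment who have not reached the first scan.
- Protocol 10.6.2.2: having no adequate post-baseline assessment is a reason for a Not Evaluable best response. It is not a reason for removal.
- Protocol 10.6.2.3: responders are "divided by the total number of patients".
- SAP 3.1.7: "patients in the Efficacy Analysis Set who do not have sufficient on-study tumor assessments to characterize response will be included in the denominator", and they count as non-responders.

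The B5 interim at 60 patients flags futility if the probability of a difference of at least 15 points is below 0.1. The rule is labelled non-binding.

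**The concern.** Dividing by 0.9 protects power only if the lost 10% drop out of numerator and denominator together and leave 180 analysed patients. If they stay as non-responders, both arms' rates shrink, and so does the difference.

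Two features of the design amplify the loss. The control prior, described as "equivalent to a control response rate of 20"%, is tight and does not shrink with the data. The futility target stays at 15 points while the difference that can be observed is smaller.

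At stake is the power claim for the study's only randomised comparison, and the chance that an effective combination is flagged futile at 60 patients.

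**Working it through.** **Inputs from the protocol (10.2, 10.6.2.1).** 2:1 allocation. Logit model with treatment and CPS. Priors N(-1.45, 0.16²), N(0, 1) and N(0, 0.1²). Laplace approximation. Success if Pr(β1 > 0) > 0.95. Futility look at 60 patients.

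**Inputs assumed.** CPS strata split 50:50 with no CPS effect. True control rate 20 to 21%, with treatment 15 points higher. The documents do not state the true control rate used in their simulations. The prior centre is 1/(1 + e^1.45) = 19.0%.

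**Step 1: the inflation.** 180/(1 − 0.10) = 200, as printed.

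**Step 2: reproduce Table 10-1.** An ordinary two-proportion calculation (60 v 120 patients, 20% v 35%) gives 54.7% power at two-sided 0.05 and 67.6% at one-sided 0.05, so the printed 90% depends on the Bayesian model. I simulated that model with 20,000 to 40,000 trials per cell. With control 21%:

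| N | Power, printed | Power, stop applied | Power, no stop | Type 1, printed | Type 1, stop applied | Type 1, no stop |
|---|---|---|---|---|---|---|
| 60 | 72.16% | 71.7% | 71.7% | 5.3% | 5.6% | 5.6% |
| 120 | 87.57% | 86.8% | 91.9% | 4.68% | 4.9% | 6.2% |
| 180 | 90.07% | 89.5% | 97.6% | 3.91% | 4.1% | 6.2% |
| 204 | 90.43% | 90.1% | 98.5% | 3.69% | 4.0% | 6.5% |

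With the stop applied, power matches within about 1 point in all seven rows tried, and type 1 error falls with N as printed. Without the stop, power is far too high and type 1 error rises. At control 20% with the stop, power at 180 is 87.1%, about 3 points below the table.

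**Step 3: apply the plan's own rule.** With 10% of patients unassessed, each rate is multiplied by 0.9:

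- Control 21%: 0.21 × 0.9 = 18.9%; 0.36 × 0.9 = 32.4%; difference 13.5 points.
- Control 20%: 0.20 × 0.9 = 18.0%; 0.35 × 0.9 = 31.5%; difference 13.5 points.

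| Scenario | Control 20% | Control 21% |
|---|---|---|
| 180, none lost, stop applied | 87.1% | 89.7% |
| 200, 5% non-responders, stop applied | 81.7% | 85.2% |
| 200, 10% non-responders, stop applied | 74.5% | 78.3% |
| 180, none lost, stop ignored | 96.5% | 97.6% |
| 200, 10% non-responders, stop ignored | 90.5% | 92.7% |
| Futility flag under target effect, none lost | 11.2% | 9.1% |
| Futility flag under target effect, 10% non-responders | 21.5% | 18.4% |

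If half the losses occur before dosing, 190 patients are analysed and 10 of them are forced non-responders. Power is then 84.5% (control 21%, stop applied).

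**Step 4: would more patients help?** The look at 60 does not depend on the final N, so with the stop applied power cannot exceed one minus the flag rate. At control 20% with 10% non-responders, N = 360 gives 77.8%, against a ceiling of 100 − 21.6 = 78.4%. Adding patients does not restore 90%.

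**The case against.** Five points can be made on the other side.

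1. **The futility rule is non-binding.** Interim decisions rest on clinical and regulatory input. If the flag is ignored, power stays at 90.5 to 92.7% even with all 10% as non-responders. This stands, so a reader should not infer that 200 patients fail to give 90% power whatever happens. But without the stop, 180 patients with no losses give 96.5 to 97.6%, so the printed 90% does not appear to be that quantity. Power falls on either basis.
2. **The planning rates may already count unassessed patients as non-responders.** The protocol's response rate uses all patients, and it does not say how the cited pembrolizumab trial's 20% was computed. If they do, nothing is diluted, and Table 10-1 gives 90.36% at 192 and 90.43% at 204. This stands. It is tempting to add that the inflation would then have no purpose, but randomised patients who are never dosed do leave the Efficacy Analysis Set, so it would have some.
3. **Not every loss is a forced non-response.** Patients lost before dosing leave the set, and those lost after a qualifying response still count as responders. This stands, and 10% is the upper end of the allowance.
4. **The explicit non-responder sentence is in a SAP with no B5 analysis.** The SAP plans no randomised comparison and no hypothesis test. Protocol 7.2.7 only calls a lost patient's later data missing. This stands in part: for B5 the rule follows from protocol 10.4.4, 10.6.2.2 and 10.6.2.3 but is not spelled out in 10.6.2.1.
5. **No sentence says that 200 preserves 90% power.** Correct. A reader will infer it from two statements placed together, and the definitions do not support that inference.

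**Conclusion.** The loss allowance and the analysis rule do not fit together as written. The division is right; the assumption behind it is not the plan's own.

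The size is conditional on two things: that the planning rates (about 20 to 21% v 35 to 36%) are rates in assessed patients, and that the interim stop is applied. The first is unstated. The second is inferred from reproducing the table. On that basis, 200 randomised give about 75 to 78% power at 10% and about 82 to 85% at 5%, against a printed figure of about 90%. The range also reflects the unstated control rate: at 10%, controls of 19% and 22% give 69.6% and 81.6%.

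A reader might go further and conclude that the trial is underpowered outright, or that non-responder scoring is the mistake. The documents support neither. The shortfall depends on the conditions above, and the scoring rule is sound. SAP section 6 records no B5 patients, so no reported result is affected.

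**What to change.** In protocol 10.2 and the synopsis:

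- State whether the assumed response rates count unassessed patients as non-responders.
- State whether Table 10-1 includes futility stopping, and give the true control rate used.
- Re-run the table with losses scored by the plan's own rule.
- Report power at 200 randomised for 0%, 5% and 10% unassessed, with and without the futility stop, and restate the power accordingly.

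Keep the non-responder rule and add no patients. The cost is one re-run of an existing simulation and a few lines of text. If the planning rates prove to be rates in assessed patients, the restated power will be less favourable.
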